Each subject will be given a unique identifier that will have no personal information linked after assignment of a randomly computer-generated list of three repeated numbers which will be available. The request for assignment will be emailed to the Data Coordinator with a completed eligibility form, and no personal identifiers except for initials and a last 4 digits of social security. The Data Manager will assign a number and the next sequential group assignment with each subsequent request will be placed in sealed envelopes. These sealed envelopes will be provided to the pharmacist will dispense the Timoptic-XE® or non-biologically active gel hydrogel for the patients according to the arm to which they have been randomized. Subject demographics will not be provided until this assignment is complete. Participants will be randomly placed into Group A (SOC plus Timoptic-XE®) or Group B (SOC plus non-biologically active gel). There will be an estimated of 24 patients in each group. The patients will not be informed of treatment administered.

Withdrawal:

The subjects may withdraw from the study at any time during the study, upon request. The investigator may also discontinue a subject if it is determined that the subject has not responded to therapy or adverse event occurred, which requires alternative therapy, or the patient displays non-compliance with study schedule. Those subjects that have undergone treatment will be followed and documented until end of the study. If there is more than 10 percent loss to follow-up, then investigators will attempt to recruit additional subjects.

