- If ulcers heal sooner than 12 weeks, the subject will be assessed the following week for a confirmatory visit, followed another week later by a 2nd confirmatory visit. Ulcer healing is defined by 100% epithelialization as determined by the clinician. The subject with healed ulcer will also return for follow-up visits Weeks 19, 23, 27 & 31 (visits 16, 17, 18 and 19).
 - Vapometer recordings will be collected on visits corresponding to weeks 19, 23, 27, and 31 on the newly healed ulcer site, 5 cm away from healed ulcer site. Readings on the contralateral side will also be marked and taken and recorded. **5 recordings for each site will be taken and the average will be documented.

NOTE: if ulceration remains open after the 12th week of application – then will switch back to standard of care and the subject will be followed monthly until completion of the study.

Blood samples will be taken on each subject on weeks 4, 8 and 12 to determine serum Timolol level. We do not anticipate blood levels in our patients to be higher than those seen in patients who receive Timoptic XE® gel for ocular indication (normal range: 0.3-0.5 ng/ml). We will terminate study on patients in whom Timolol level is 0.7 ng/ml or higher.

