6. STATISTICAL DESIGN

Measures:

Measures will be collected at baseline, weekly thereafter, with primary endpoint of complete healing at Visit 14/Week 14, and final secondary endpoint measurement at Visit 17/Week 31. The ulcer will be assessed weekly and will be treated as described above. A designated inter-observer (blinded to the treatment of the subjects) will regularly review images and physical exam findings to determine primary and secondary endpoints. The following measurements will be taken: size (surface area calculation), photos (digital includes ruler) and complete foot ulcer assessment (description of ulcer/characteristics), before and after debridement. Subjects where ulceration healed earlier than Visit 14/Week 14 will have follow-up assessment one week after healing, a 2nd assessment a week after, then 4 monthly visits at Weeks 19, 23, 27 & 31. If the ulceration healed after 12 weeks, then the subjects will be similarly assessed. The subject with healed ulcer will also return for follow-up visits Weeks 19, 23, 27 & 31 (visits 16, 17, 18 and 19).

During the study, if ulceration appears to be infected as determined by clinical presentation characterized by the presence of two or more signs of inflammation, the clinician will follow the protocol of obtaining wound culture for microbiology, radiographs, blood work (CBC, chemistry panel, sedimentation rate, and C-reactive protein), and treatment immediately with appropriate antibiotics. Subjects with infected ulcers will be withdrawn from study and investigators will be notified. In addition, adverse events will be well documented and treated per protocol, and subjects will be withdrawn from study.

Clinical Outcomes:

- The percentage of subjects that have complete closure of ulceration by Visit 14/Week 14 and Visit 17/Week 31. Complete healing will be defined as full re-epithelialization with no drainage, or callus formation and remains closed after 1 week of wound closure.

- Rate of wound healing to achieve complete closure. Weekly measurements of surface area will be recorded using Silhouette Mobile™ ulcer tracing and surface area calculation.
- A diabetic foot ulcer assessment form will be filled out at weekly follow-up visits, that describes characteristics of ulceration including peri-ulcer erythema, wound margins, fibrin, granular tissue, peri-ulcer pruritus, edema and location, pain, amount of drainage and type, amount of epithelialization, pain level, depth, and bioburden.

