- Number of incident subjects with infection, osteomyelitis and acute Charcot during the study, will be withdrawn from the study.
- Number of incidences of adverse effects will be reported from all sites and will be withdrawn from the study.
- VR-36 Health Survey, and the Lower Extremity Functional Scale Outcome Questionnaire (self-administered questionnaires) will be used to measure quality of life and provided at beginning of the study and at the study endpoint.
- Rate of transepidermal water loss will be measured weekly subsequent to wound closure and compared in the two groups.

Sample Size Estimation:

From previous studies, we expect that about 20% of the study subjects will heal in the control arm of our study by the 12th week of care. We estimate that the experimental treatment will improve this outcome with 63% of the study subjects healing by the 12th week of care (a healing rate close to that reported in the most recent case series of topical use of timolol on chronic wounds).

We will perform simple allocation of the subjects using an electronic randomization for treatment assignment-since our target enrollment population is fairly homogenous.

The sample size calculation will require the enrollment of 48 subjects (24 subjects in each arm) to provide a power of 80% to detect a difference of 43% (= 63% - 20%) in the rate of ulcer healing between the two arms by using two-sided Fisher's exact test at a significance level of 5%. It is estimated that the overall attrition will be 35%. Specifically, 10% of the subjects who are enrolled will be exited from the study prior to randomization, 10% will not meet the primary endpoint analysis inclusion requirement and 15% will not complete the study due to other factors such as treatment failure, loss to follow-up, adverse events, clinical/safety issues, and/or non-compliance. We will track the various reasons for study exit. Therefore, 138 subjects (69 subjects in each arm) will be recruited into the study after taking into account the overall attrition of 35%.

The consulting statistician will review implementation and compare major baseline demographic and prognostic characteristics to ascertain that randomization was successful. The power analysis was formulated using the STPLAN Version 4.5 (2010) with the input of the study consultant biostatistician.

Analyses:

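### Section 6 withdraws subjects from the study for infection or any adverse event, Section 3 makes this discretionary and keeps following treated subjects, and nothing says which rule governs

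*Combined protocol and SAP*

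**What the plan says.** Section 6 (Measures) states a mandatory rule twice. For infection: "Subjects with infected ulcers will be withdrawn from study and investigators will be notified". For adverse events generally: "adverse events will be well documented and treated per protocol, and subjects will be withdrawn from study". The Clinical Outcomes list in the same section repeats it, adding osteomyelitis and acute Charcot, and ends with a garbled line: "Number of incidences of adverse effects will be reported from all sites and will be withdrawn from the study". None of these sentences limits the rule by severity, seriousness or relationship to study gel.

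Section 3, under Withdrawal, is permissive: "The investigator may also discontinue a subject if it is determined that the subject has not responded to therapy or adverse event occurred". The sentence goes on to restrict this to events that call for alternative therapy. It is followed by "Those subjects that have undergone treatment will be followed and documented until end of the study" and then "If there is more than 10 percent loss to follow-up, then investigators will attempt to recruit additional subjects".

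Section 4.3.3 separates stopping gel from leaving the study in one situation only. For an ulcer still open after 12 weeks of application, the plan "will switch back to standard of care and the subject will be followed monthly until completion of the study". The same section schedules the primary safety measurement: "Blood samples will be taken on each subject on weeks 4, 8 and 12 to determine serum Timolol level".

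**The concern.** A mandatory rule and a discretionary rule cannot both govern the same event. The plan also does not say whether *withdrawn* means off gel or out of observation.

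If Section 6 is applied as written, a mild, unrelated event ends participation. Several things are then missing because of that event:

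- Week 14 closure, when the ulcer is still open at exit;
- later vital signs, which feed the secondary safety outcomes;
- later new adverse events, so the planned regression on each event type (Section 6, Analyses) cannot see types that follow a subject's first event.

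Later serum timolol is lost only for subjects who would otherwise have stayed on gel. Once gel has stopped, later samples say little about exposure.

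Infection exits are unlikely to be unrelated to the primary outcome, since Section 1 itself ties longer non-healing to a higher risk of infection. The Analyses text does not say how a withdrawn subject enters the Fisher comparison or the Kaplan-Meier curves. Recruiting additional subjects restores numbers but not these data.

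**Working it through.** **Texts side by side**

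| Question | Section 6 | Section 3, Withdrawal |
|---|---|---|
| Is exit required? | Yes | At the investigator's discretion |
| Which adverse events? | Any | Those needing alternative therapy |
| Follow-up afterwards? | Not stated; exit is from the study | Treated subjects followed to the end |

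**Inputs from Section 6, Sample Size Estimation**

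- Closure by week 12: 20% control, 63% timolol.
- Two-sided Fisher's exact test at 5%; 24 per arm for 80% power.
- 15% non-completion from several causes combined, adverse events among them.
- 69 per arm recruited, with 10% of enrolled subjects leaving before randomisation: 69 × 0.90 = 62.1, taken as 62.

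**Assumptions, not in the documents**

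- A weekly event risk r, equal in both arms and unrelated to healing.
- A constant weekly closure chance c; the one-week confirmation of closure is ignored.
- Anyone who leaves before closure counts as not closed.

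**Step 1: the plan's own figure.** Enumerating both binomials gives exact Fisher power of 79.5% at 23 per arm and 82.5% at 24, so 24 per arm reproduces. At 62 per arm, power is 99.9%.

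**Step 2: weekly closure chance.** c = 1 − (1 − P)^(1/12). Timolol: 1 − 0.37^(1/12) = 0.0795. Control: 1 − 0.80^(1/12) = 0.0184.

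**Step 3: closed and left by 12 weeks.** Let s = (1 − r)(1 − c) and A = (1 − s^12)/(1 − s).

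- Event first within a week: closed = (1 − r)cA; left = rA.
- Closure first within a week: closed = cA; left = (1 − c)rA.

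Example, timolol, r = 0.02, event first: s = 0.98 × 0.9205 = 0.9021; s^12 = 0.2903; A = 0.7097/0.0979 = 7.25; closed = 0.98 × 0.0795 × 7.25 = 0.565; left = 0.02 × 7.25 = 0.145.

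**Step 4: match to the planned 15%.** Leaving averaged over the arms equals 15% at r of about 1.74% (event first) or 1.83% (closure first). Bracketing these:

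| r, order | Left: timolol / control (mean) | Closed: timolol / control | Power, 24 per arm | Power, 62 per arm |
|---|---|---|---|---|
| 1.75%, event first | 12.8 / 17.3 (15.1)% | 57.2 / 17.9% | 75.2% | 99.5% |
| 1.75%, closure first | 11.8 / 17.0 (14.4)% | 58.3 / 18.2% | 76.7% | 99.6% |
| 2%, event first | 14.5 / 19.6 (17.0)% | 56.5 / 17.7% | 74.2% | 99.4% |
| 2%, closure first | 13.3 / 19.2 (16.3)% | 57.6 / 18.0% | 75.9% | 99.5% |

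**Step 5: sensitivity.** A cruder version removes 15% of would-be healers in each arm (0.85 × 63% = 53.6%; 0.85 × 20% = 17%). It gives 69.1% at 24 per arm and 98.9% at 62. Excluding leavers at r = 2% gives 76–77% at 24 per arm, but it raises apparent closure: 0.565/0.855 = 66% and 0.177/0.804 = 22% (event first), against the planned 63% and 20%. How leavers are counted therefore changes the estimate even when risk is equal and unrelated to healing.

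**The case against.** The best defence is that Section 3 holds the operative rule. It carries the Withdrawal heading, limits adverse-event exits to those needing other therapy, and its follow-up sentence most naturally describes withdrawn subjects who had been treated. The visit schedules record adverse events through Week 31, and Section 4.3.3 has its own stopping threshold for serum timolol (0.7 ng/ml or higher). Both fit poorly with an exit at the first mild event. The Clinical Outcomes lines are garbled and may be loose drafting. All of this stands as evidence of what the authors probably meant for adverse events; the infection wording is clearer.

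It does not resolve the conflict. Section 6 says withdrawn from the study, not from treatment. The sample size text counts adverse events among reasons for not completing. Section 4.3.3 states continued follow-up where it is intended, and Section 6 has no such sentence. Section 5 follows an affected subject until the event resolves, which is not the same as keeping the scheduled visits. Passive chart follow-up is defined for patients who were not randomised.

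A reader might go further in four ways that the documents do not support:

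- *Observation certainly ends at the first event.* Section 3 can be read the other way.
- *The triggering event is lost.* Section 5 has it recorded and followed.
- *Power collapses.* Weekly risks of 5% or 10% would give 63–67% or 48–55% at 24 per arm, but they imply 35–37% or 57–59% leaving, far above the planned 15% from all causes.
- *Different sites will apply different rules.* The Protocol Summary names one centralised study location, although other sections mention facilities and sites.

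**Conclusion.** The contradiction is real, is in current text, and should be fixed. Its size cannot be stated, because the documents give no adverse-event or infection rate; nor can the direction of any bias. If Section 3 governs, the consequence is small. If Section 6 governs, data go missing because of an earlier event, and for infection that event is probably related to healing.

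Power is secondary. With the whole 15% allowance treated as event withdrawals and leavers counted as not closed, the weekly model gives about 74–77% at 24 per arm (69% in the cruder calculation), against 82.5% with no loss. At 62 per arm it stays above 99%. These figures assume equal risk in both arms, unrelated to healing. They turn mainly on how many subjects are randomised, and the plan gives both 24 per arm and a recruitment target of 69 per arm. The missing later safety data do not depend on that number.

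**What to change.** Replace the withdrawal wording in Section 6 (Measures and Clinical Outcomes) with a rule consistent with Section 3. An ulcer infection or adverse event may lead to stopping study gel, and stopping may stay mandatory for infection if the investigators wish. It does not end participation: scheduled visits and assessments continue to Week 31 unless the subject withdraws consent.

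Add one line to Section 6, Analyses: such subjects stay in the Week 14 closure comparison in their randomised arm with their observed outcome, and no documented closure counts as not closed.

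The cost is a short edit in these places and continued follow-up of subjects who are off gel, at visits already scheduled. Clinical protection is unchanged, since gel can still be stopped and infection treated at once.

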1.1. STUDY FLOW CHART

Study Plan Schematic

Procedure	Screening Phase Visits 1-2 (Week 1-2)		Active Phase Visits 3-14 (Week 3-14) Including a 1st confirmatory visit if healed before 12 weeks of treatment		2nd Confirmatory Visit Prior to Follow-up Phase Visit 15 (Week 15)	Follow-up Phase Visits 16, 17, 18 & 19 (Week 19, 23, 27 & 31)			
	Visit 1 (Week 1)	Visit 2 (Week 2)	Visit 3 (Week 3) Randomization	Visits 4-14 (Week 4-14) Study Endpoint at Week 14*	Visit 15 (Week 15)	Visit 16 (Week 19)	Visit 17 (Week 23)	Visit 18 (Week 27)	Visit 19 (Week 31)
Inclusion/Exclusion Criteria	X	X	X						
Informed Consent/HIPAA document	X								

VR-36 Health Survey Questionnaire	X			X*					
Lower Extremity Functional Scale Outcome Questionnaire	X	X		X					X
Charlson-Comorbidity Index	X								
Physical Exam	X			X*					
EKG	X			X*					
Vital Signs	X	X	X	X	X	X	X	X	X
Ankle-Brachial Index/Duplex Scan	X	X							
Debrided Tissue for genetic analysis (Weeks,1-9)	X	X	X	X					
Bacterial, Fungal Infection and Malignancy Evaluation	X								
Laboratory evaluation (hematology, renal, and liver function)	X								
Vapometer Readings@ (@If healed, readings recorded from point of closure + 4 months)				X@	X	X	X	X	X
Blood Sample for Timolol assay/Inflammatory markers(weeks 4,8,12)	X			X†					
Ulcer Assessment	X	X	X	X	X	X	X	X	X
Debridement († if needed)	X	X	X	X	X†	X†	X†	X†	X†
Ulcer Photography and Area Measurement	X	X	X	X	X	X	X	X	X
Offloading device	X	X	X	X	X	X	X	X	X
Randomization			X						
SOC + Timoptic-XE@ or SOC + non biologically active gel (hydrogel as placebo medication)			X	X					

SOC			X	X	X	X	X	X	X
Concomitant Medications and Adverse Events	X	X	X	X	X	X	X	X	X

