The primary outcome is complete ulcer closure by Week 14 (end of the Active Phase) of the study and the rate of ulcer healing by the 12th week of care between the two arms.

[figure not shown]
Hypothesis to be tested: The null hypothesis is that there is no difference in the proportion of subjects with complete wound closure of DFU between the timolol treatment group and the control group. Complete wound closure is defined as 100% closure, or skin re-epithelialization without any drainage present or dressing requirements. Two-sided Fisher's exact test will be used to compare the proportion of complete ulcer closure by Week 12 (end of the Active Phase) of the study and the rate of ulcer healing by the 12th week of care between the two arms. The Kaplan-Meier method will be used to estimate the survival function of time to achieve complete ulcer closure (if less than 12 weeks) for each arm, and a two-sided log-rank test will be used to compare the survival curves between the two arms.

The area of the target ulcer will be summarized by treatment group and visit. Both actual value and change from the previous visits ulcer area will be presented. A second summary of target ulcer area will also be given which will present change from baseline. The weekly change and the percentage weekly change in the target ulcer area from visit to visit will be summarized by treatment group and visit. The two-sided t-test or Wilcoxon rank-sum test as appropriate will be used to compare relative ulcer area from baseline to Week 12 between the two arms.

Chi-square test or Fisher's exact test as appropriate will be used to compare wound healing rates in relationship to wound size, as well as wound healing rates between the treatment groups at the 4-week follow-up and at the 12-week follow-up period and recidivism rate.

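### TEWL has three conflicting schedules, and fixed-week TEWL readings or a crude recidivism test would give timolol healers more time since closure than control healers

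*Combined protocol and SAP*

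**What the plan says.** The Protocol Summary lists change in TEWL after wound closure among the secondary efficacy outcomes, and its data analysis text compares TEWL in healed ulcers between arms. The timing is given in three ways:

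- **Section 6, Clinical Outcomes:** "Rate of transepidermal water loss will be measured weekly subsequent to wound closure and compared in the two groups".
- **Section 4.3.3:** "Vapometer recordings will be collected on visits corresponding to weeks 19, 23, 27, and 31 on the newly healed ulcer site". Sections 4.3.4 and 4.3.6 repeat these four weeks.
- **Study Flow Chart:** Vapometer readings are marked at Visits 4-14 if healed and at Visits 15-19, with the note "readings recorded from point of closure + 4 months".

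No passage names the visit at which TEWL is compared, the reference value for the change, or a model.

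Recidivism appears in the data analysis part of the Protocol Summary and in Section 6, Analyses. Chi-square or Fisher's test is to compare healing rates "at the 4-week follow-up and at the 12-week follow-up period and recidivism rate". It has no definition, denominator or time window.

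Healers have confirmatory visits one and two weeks after healing, then fixed visits ending at Week 31. Late healers are included: "If the ulceration healed after 12 weeks, then the subjects will be similarly assessed". Under Section 4.3.3, ulcers still open after 12 weeks of application go back to standard of care in both arms.

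**The concern.** The schedules produce different data. After Week 15 the visits are four weeks apart, so weekly readings are not possible on the planned visits. An ulcer that closes at Week 6 would be read from Week 6 under the flow chart, but first at Week 19, 13 weeks after closure, under Section 4.3.3. Staff following different sections would collect readings that cannot be pooled.

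The fixed-week schedule also ties treatment arm to time since closure. If timolol speeds closure, as the trial supposes, its healers have been closed longer at any given study week. If TEWL falls as closed skin matures (an assumption; the documents give no figure), timolol would look better without any effect on the barrier. Crude recidivism would err the other way, because timolol healers would have had longer in which to reopen. Both comparisons are also made in a subset defined after randomisation and expected to differ in size between arms.

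**Working it through.** **Inputs from the documents.** Section 6: "we expect that about 20% of the study subjects will heal in the control arm of our study by the 12th week of care" and, for timolol, "with 63% of the study subjects healing by the 12th week of care". The sample size is "enrollment of 48 subjects (24 subjects in each arm) to provide a power of 80" percent, with a two-sided Fisher's exact test at 5%. Treatment starts at Week 3, so Weeks 19, 23, 27 and 31 are 16, 20, 24 and 28 weeks after randomisation.

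**The plan's own figure.** Exact two-sided Fisher power for 20% v 63% is 79.5% at 23 per arm and 82.5% at 24. The 24 per arm is reproduced, so these rates are the design rates.

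**Hazards (constant hazard is an assumption).**
- Control: −ln(0.80)/12 = 0.0186 per week.
- Timolol: −ln(0.37)/12 = 0.0829 per week.
- Cross-check: the control hazard implies 1 − 0.80^(20/12) = 31% healed at 20 weeks, the figure the Background gives for good wound care.

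**Mean closure time among those closed by T weeks:** 1/λ − T·e^(−λT)/(1 − e^(−λT)).
- Closures within 12 weeks: control 53.78 − 12 × 0.80/0.20 = 5.8; timolol 12.07 − 12 × 0.37/0.63 = 5.0. The gap is 0.8 week.
- Control by 28 weeks: 53.78 − 28 × 0.594/0.406 = 12.8, so mean time since closure is 28 − 12.8 = 15.2 weeks.
- Timolol by 28 weeks, reverting to the control hazard after 12: 0.63 close early (mean 5.02). A further 0.37 × 0.257 = 0.095 close late (mean 12 + 7.60 = 19.60). The overall mean is (0.63 × 5.02 + 0.095 × 19.60)/0.725 = 6.9, so time since closure is 21.1 weeks.

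Mean weeks since closure among healers:

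| Visit | Control | Timolol, reverts | Gap | Timolol, constant | Gap |
|---|---|---|---|---|---|
| Week 19 | 8.4 | 10.6 | 2.2 | 9.7 | 1.3 |
| Week 23 | 10.6 | 14.2 | 3.5 | 12.6 | 2.0 |
| Week 27 | 12.9 | 17.6 | 4.8 | 15.7 | 2.9 |
| Week 31 | 15.2 | 21.1 | 5.9 | 19.0 | 3.8 |

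Weibull shapes from 0.5 to 3, with no change of hazard at 12 weeks, give a gap of 2.5 to 6.1 weeks at Week 31 and 0.5 to 0.8 week for closures within 12 weeks.

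**Size of the healed subset.** By 12 weeks: 24 × 0.20 = 4.8 control v 24 × 0.63 = 15.1 timolol. By Week 31, with reversion: 9.7 v 17.4, of whom 51% v 13% closed after 12 weeks.

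**Crude recidivism by Week 31.** Assume the same reopening hazard h in both arms. An ulcer closing t weeks after randomisation has reopened with probability 1 − exp(−h(28 − t)), averaged here over the closure times. The range for h is an assumption.

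| h per week | Control | Timolol, reverts | Gap (points) | Timolol, constant | Gap (points) |
|---|---|---|---|---|---|
| 1% | 13.8% | 18.8% | 5.0 | 17.1% | 3.2 |
| 2% | 25.3% | 33.9% | 8.6 | 30.9% | 5.6 |
| 3% | 34.8% | 45.9% | 11.1 | 42.0% | 7.3 |

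For closures within 12 weeks only, the gap is 0.6 point at 1% (20.5% v 19.9%) and 1.2 points at 3% (49.5% v 48.4%, before rounding).

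**The case against.** A reader might infer that timolol skin will be judged about six weeks later after closure than control skin. The documents do not support that as a general statement. Two of the three TEWL schedules start at closure, and no passage says at which visit the arms are compared. The six-week figure needs the fixed-week schedule, the last visit, late healers and, under constant hazards, a timolol hazard that drops to the control level after 12 weeks. The return to standard of care makes that drop plausible, but the documents do not state it.

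A reader might also infer that the recidivism test is known to be biased. The plan gives no denominator or window; counting all healers at Week 31 is one reading of it, and the reopening hazard has no source in the documents. Nor would false positives rise much. With 17 v 10 healers and the reverting-model rates, two-sided Fisher rejects about 1.6% of the time at h = 1% and 6.1% at h = 3%. The distortion is mainly in the estimate.

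Nor do the documents show harm to TEWL itself: they give no size for its change with time since closure, and adjacent and contralateral readings are already taken.

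These points narrow the concern. They leave standing the conflicting schedules, the undefined recidivism analysis, and the absence of any rule that times either comparison from closure or limits it to early closers.

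**Conclusion.** The schedule conflict is certain from the text and needs no assumption. The imbalance in time since closure is conditional: it arises under the fixed-week TEWL schedule, and for recidivism if it is counted at the end of follow-up. Its direction follows from faster healing on timolol; its size depends on the closure model. Under constant hazards it is 2.2 weeks at Week 19 rising to 5.9 at Week 31 with reversion, 1.3 to 3.8 without, and 0.8 for closures within 12 weeks. The matching false recidivism gap against timolol is about 5-11, 3-7 and 1 points for an assumed reopening hazard of 1-3% per week. No size can be given for TEWL. This should be corrected, but it concerns secondary comparisons and leaves the primary analysis untouched.

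**What to change.** - **Schedule.** Reconcile Section 6, Sections 4.3.3, 4.3.4 and 4.3.6, and the flow chart into one TEWL schedule that uses the visits already planned from closure onward.
- **TEWL analysis.** Analyse by time since confirmed closure in a mixed model, with the adjacent and contralateral readings as reference. At a matched time the arm gap in time since closure is then zero by construction. Label the result a non-randomised comparison among healers.
- **Recidivism.** Define reopening, and replace the crude test with a Kaplan-Meier analysis from confirmed closure to reopening, censored at the last visit. The healers-only label applies here too.
- **Supportive randomised comparison.** Add the proportion closed by Week 14 and still closed at Week 31, in all randomised subjects. It mixes healing with durability, so present it as sustained closure, not as durability alone.

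The cost is SAP wording and one schedule correction, with no added visits. Two limits should be stated. Follow-up ends 28 weeks after randomisation, so a full 16 weeks after closure fits only for closures within about 28 − 16 = 12 weeks: about 49% of control healers and 87% of timolol healers in the reverting model. Later post-closure times will therefore be observed unequally by arm. Closure dates after Week 15 are known only to within about four weeks.

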3. STUDY POPULATION

The study population includes all Veterans’ age 18 or older, with a documented diagnosis of diabetes and a foot ulceration that has existed for at least 4 weeks at the time of enrollment into the study. Diabetic patients with foot ulcers will be selected from a random sample of patients from the Multispecialty Wound Healing Clinic at Sacramento VA Medical Center, and the six clinical sites at the VANCHCS. In fact, there were over 15,146 patients with diabetes mellitus receiving care at the VANCHCS, which includes Sacramento VA Medical Center and 6 other satellite clinics, and approximately 1002 patients with DFU were receiving care at the VANCHCS, within the last 2 fiscal years.

[figure not shown]
Figure 2 illustrates the selection process with the anticipated number of participants in the study. With a minimum of 60% participation, there should be adequate recruitment for this study. The sites will accrue a total target sample of approximately 138 subjects and assuming approximately 35% dropout rate, the goal is to enroll 48 subjects in total, 24 subjects in each arm.

[figure not shown]
Selection of Cases and Controls:

The investigators will query the CPRS/VISTA database at the 7 respective sites of the VANCHCS. Eligible subjects will be called by the research coordinator and invited to participate in the study.

Those who agree will be given an appointment for screening and enrollment. A subject must meet all the following criteria to be eligible for study inclusion.

Figure 2: Summary of Selection Process

Board (IRB). We will perform simple allocation of the subjects using an electronic randomization for treatment assignment-since our target enrollment population is fairly homogenous.

Run-in phase (screening phase) in which all potential subjects are given the standard of therapy for 2 weeks, will be performed to determine compliance with return visits and performing standard of care dressings.

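### The recruitment target of 138 (69 per arm) does not follow from 48 evaluable subjects and 35% attrition; the plan's own inputs give 74 (37 per arm)

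*Combined protocol and SAP*

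**What the plan says.** Section 6 (Statistical Design, Sample Size Estimation) assumes healing by the 12th week of care in 20% of controls and 63% of timolol subjects, compared by a two-sided Fisher's exact test at 5%. It states: "The sample size calculation will require the enrollment of 48 subjects (24 subjects in each arm) to provide a power of 80" per cent.

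The same paragraph puts overall attrition at 35% and itemises it:
- "10% of the subjects who are enrolled will be exited from the study prior to randomization"
- a further 10% will not qualify for the primary endpoint analysis
- "15% will not complete the study due to other factors such as treatment failure, loss to follow-up, adverse events", among other reasons

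It then concludes, introduced by the word therefore, that "138 subjects (69 subjects in each arm) will be recruited into the study after taking into account the overall attrition of 35" per cent.

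Section 3 (Study Population) gives the same three numbers together: "a total target sample of approximately 138 subjects and assuming approximately 35% dropout rate, the goal is to enroll 48 subjects in total". Just before that it says "With a minimum of 60% participation, there should be adequate recruitment for this study". Its randomisation text adds: "There will be an estimated of 24 patients in each group". The Protocol Summary gives 48 subjects, 24 per arm, and does not mention 138.

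**The concern.** Section 6 presents a closed calculation: a required number, one loss rate, and a recruitment number said to result from them. A 35% loss should raise 48 by a factor of about 1.54 (1/0.65). The plan raises it by a factor of 2.9 (138/48). Either the loss rate or the target is wrong as written.

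What is at stake is the credibility of the stated sample size and the number of veterans the trial plans to recruit. The target is almost twice what the plan's own inputs require. The error is towards too many subjects, so the validity of the primary comparison is not at stake.

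There is also a smaller wording point. Sections 3 and 6 describe 48 as the number enrolled, the randomisation text in Section 3 puts about 24 in each randomised group, and the power statement treats 24 per arm as the number compared. With 10% of enrolled subjects expected to leave before randomisation, and more afterwards, one number cannot carry all three meanings unless losses are replaced.

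**Working it through.** **Inputs**, from Section 6 unless noted: healing 20% and 63%; two-sided Fisher's exact test, alpha 5%; 24 per arm, 48 in total; overall attrition 35% = 10% + 10% + 15%; stated target 138, 69 per arm. From Section 3: at least 60% participation.

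**1. The base of 24 per arm reproduces.** Full enumeration of the two-sided Fisher test at 20% against 63% gives power of 79.5% with 23 per arm and 82.5% with 24. The continuity-corrected formula for two proportions also gives 24. The fault is therefore in the inflation step.

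**2. Inflation for attrition.** Number to recruit = evaluable / (1 - attrition).
- Per arm: 24 / 0.65 = 36.9, so 37
- Total: 48 / 0.65 = 73.8, so 74

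**3. Reverse check of 138.**
- Evaluable after 35% loss: 138 x 0.65 = 89.7, about 90 or 45 per arm. Exact Fisher power at 45 per arm is 98.4%.
- Loss needed to end at 48: 1 - 48/138 = 65.2%
- Excess over the figure that follows: 138 - 74 = 64

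**4. What reproduces 138.** Dividing by the share lost instead of the share kept gives 24 / 0.35 = 68.6, so 69 per arm and 138 in total. The match is exact, but the plan does not show its working, so this cause is an inference.

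**5. Other routes to 138.**

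| Route | Calculation | Result |
|---|---|---|
| Multiply up by the loss | 48 x 1.35 = 64.8 | 65 |
| 48 is the number randomised; only the 10% pre-randomisation exit applies | 48 / 0.90 = 53.3 | 54 |
| Losses applied one after another | 48 / (0.90 x 0.90 x 0.85) = 48 / 0.6885 = 69.7 | 70 |
| 35% attrition, then 60% participation | 74 / 0.60 = 123.3 | 124 |
| As above, with a further 10% exit | 48 / (0.65 x 0.60 x 0.90) = 136.8 | 137 |

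Only the last comes close. It counts the 10% pre-randomisation exit twice, and the plan does not describe it.

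**6. The corrected flow.** Recruited 74; randomised 74 x 0.90 = 66.6, about 67; evaluable 74 x 0.65 = 48.1, so 48.

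**The case against.** **138 may be a screening pool.** This is the best defence. Section 3 sets accrual of about 138 beside a goal of enrolling 48, the plan follows screen failures passively without adding them to enrolment (Section 4.2, Group C), and the selection figure in Section 3 is not available in the text. A pool larger than the randomised number is clearly foreseen, and since Section 3 gives both numbers in one sentence, it would be too strong to call them rival operating targets. But Section 6 attributes 138 to the 35% attrition alone and splits it by arm, and a screening pool has no arms. The defence shows what may have been intended; it does not make the written derivation correct.

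**The per-arm wording is shorthand.** That stands. Inflating per arm before randomisation is common, and 37 per arm is used the same way here. The objection to 69 is its size.

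**70 as an equally good answer.** A reader might infer that the attrition base is left open and that sequential losses, giving 70, are as valid as 74. The documents do not support this. The three components add to exactly the stated 35%, whereas sequential losses amount to 1 - 0.6885 = 31.2% and contradict it.

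**A loss of power.** A reader might also infer that the trial is underpowered, on the argument that 48 are enrolled and 35% of them lost, leaving about 31 (48 x 0.65 = 31.2). The documents do not support that either. In Section 6 the 48 comes before the inflation and the larger recruitment number is meant to absorb the loss. The power-loss reading sets that target aside and needs every loss to leave the analysis unreplaced, which the plan does not say. Under Withdrawal, Section 3 says: "If there is more than 10 percent loss to follow-up, then investigators will attempt to recruit additional subjects". Treatment failure, listed within the 15%, may be an observed non-closure rather than missing data.

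**Conclusion.** The stated target of 138 (69 per arm) is wrong as written in Section 6 and repeated in Section 3. From 48 evaluable subjects and 35% overall attrition, the figure is 74 (37 per arm). The plan therefore overstates recruitment by 64 subjects, a factor of 138/74 = 1.86. With 138 recruited and the stated attrition, power would be about 98% against a design value of 80%.

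This rests on two readings of Section 6: that 35% is the total loss from the number recruited, as its itemisation implies, and that 48 is the number left for the primary comparison, the reading under which inflating it makes sense. The base calculation of 24 per arm is sound. The error does not threaten the primary inference. It should be corrected because a stated sample-size figure does not follow from its own inputs. The inconsistent label for 48 is a secondary wording point.

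**What to change.** In Sections 3 and 6, replace 138 (69 per arm) with 74 recruited, about 67 randomised and 48 evaluable, and show the step 48/0.65 = 73.8.

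If 138 was intended as a screening pool, or if a loss of about 65% was really expected, say so, give the basis, and remove both the 69 per arm and the derivation from 35%.

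In the Protocol Summary, Section 3 (recruitment and randomisation text) and Section 6, label 48 (24 per arm) consistently as the number evaluable for the primary comparison. Where the text means the number enrolled or randomised, give that number separately.

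The cost is a short text amendment. The sponsor has to confirm what 138 was meant to count. No procedure or analysis changes.
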